Aim 1: Determine the impact of the *Compañeros en Salud* (Partners in Health) curriculum in conjunction with RT-CGM on glycemic control in Latinx patients with T2D. We will enroll 100 Latinx patients with uncontrolled T2D through a federally funded healthcare network across the Seattle region. Participants will be randomized to receive the *Compañeros en Salud* diabetes self-management education and support (DSMES) intervention with or without RT-CGM (n=50 per group) over 12 weeks with an additional 12 weeks of follow-up.(control= blinded -CGM+ Education and intervention= RT-CGM + education). Study visits will be held at screening, baseline(0-4 weeks) and 12 weeks (+/- 2 weeks) and 24 weeks (+/-2) weeks. Participants in the blinded -CGM+ Education group will undergo blinded CGM for 1 week at baseline and for 10 days after each study visit. The primary outcome will be A1C. Secondary outcomes will include time in range as measured by CGM and other CGM indices, body mass index, waist circumference, and systolic and diastolic blood pressure.

Aim 2: Engage key stakeholders to optimize acceptability and minimize barriers to participation in the intervention. After 25% of participants have completed the intervention, we will convene a committee of stakeholders that includes study participants (both completers and non-completers), community providers, diabetes educators, and patient navigators. Key barriers and facilitators to the intervention will be identified by stakeholders, and the intervention will be amended based on stakeholder feedback. The impact of these revisions on participant engagement during the study intervention will be analyzed.

Aim 3. Determine the effects of the *Compañeros en Salud* curriculum with or without adjunct RT-CGM on diabetes-related behaviors and distress. At baseline and 12-+2 weeks and 24 +/- 2 weeks, participants will complete surveys capturing dietary behaviors, physical activity, and diabetes-related distress. Participants will be provided with pedometers, and activity data will be captured for 10 days following each study visit. **Sub-aim 3A:** As an exploratory sub-aim, we will examine behavioral changes in other members of participants' households through brief surveys. This sub-aim will provide preliminary data regarding a possible "ripple effect," the capacity for an intervention in 1 individual to affect health-related behaviors in other household members.

B. Background

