The study screening and research procedures will take place at the patient's home or in the health education office, or another Sea mar Clinic location, per patient preference. If possible, the visit will be performed in person, but given the increase in tele-health visits during the COVID pandemic, if a potential participant is unable to complete the screening visit and/or research visits in person, then tele-visits for the research visits will be offered.

Population:

We propose to perform an observational prospective study that will involve 100 subjects with confirmed type 2 Diabetes. There will be 50 participants in the RT-CGM+education intervention group and 50 in blinded-CGM+education group. Patients with type 1 diabetes as well as controlled diabetes <8.0 % will be excluded (8.0 or greater included). Sea Mar clinics care for more than 8,500 patients living with diabetes, and when the designated clinics were reviewed for Latinx patients with A1C ≥8.0%, over 460 potential participants were found. Thus, we will have a robust population for recruitment and diabetes self-empowerment. Additionally, participants may be found in the local community or UW clinics

E. Statistical Considerations

Sample Size Estimation

In this study, we plan to enroll and include a total of n=100 study participants. The study is designed and sized first for assessing the primary endpoint of change in A1C from baseline to 12 weeks (Aim 1), and secondarily to assess the impact of RT-CGM on A1C. To assess statistical power, we assumed a standard deviation in baseline A1C of 1.2 and a reduced standard deviation of 1.0 at 12 weeks to reflect an anticipated reduction in A1C due to the *Compañeros en Salud* curriculum. We further assume a correlation in A1C measurements of $r=0.5$, which is likely to be higher and will result in greater statistical power. Finally, assuming a 15% reduction in the effect sample size (n=85) due to attrition, the study is sized to detect reductions in A1C of 0.4 or larger with 90% statistical power. If the actual correlation between baseline and week 12 HbA1c measurements is $r=0.7$ or higher, the study has 90% power to detect differences in A1C as small as 0.3. Under similar assumptions, the study is sized to detect a 0.6 difference in 12-week HbA1c between subjects randomized to RT-CGM vs blinded CGM (power = 0.82 assuming $r=0.5$; power=0.93 assuming $r=0.7$). A two-sided type 1 error rate of 0.05 was assumed throughout.

Data Analysis Plan

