AIM 1: Our primary endpoint for Aim 1 is the change in A1C from baseline to 12+/-2 weeks (end of the intervention period). Secondary outcomes include between-group differences in change in A1C at

24+/-2 weeks and changes in body weight, BMI, and blood pressure at 12+/-2 and 24+/-2 weeks. We will use simple descriptive statistics to quantify between-group differences in changes in CGM indices including TIR, mean glucose, mean amplitude of glycemic excursions, TAR, TBR, and coefficient of variation. The primary outcome of A1C will be assessed using a random-intercept random-slope linear mixed effects regression model that adjusts for an indicator of RT-CGM and time (baseline, visit 2, and visit 3) as fixed effects. To assess the effectiveness of the *Compañeros en Salud* curriculum, inference for Aim 1 will focus on the change in A1C from baseline to 12 weeks for the entire cohort (regardless of RT-CGM status). Secondary outcome measures of TIR, body mass index, waist circumference, and systolic/diastolic blood pressure will be similarly assessed using a generalized linear mixed effects model appropriate for each type of outcome measurement.

We will conduct a missing data analysis to describe and characterize enrolled participants who do not provide data due to attrition. Linear mixed effects models naturally handle intermittent missing data through maximum likelihood estimation. As described by Molenberghs and Kenward,⁴⁹ we will use inverse probability weighting in secondary analysis within each longitudinal regression model to inflate the weights of cases that are underrepresented in the analysis due to selective attrition and/or non-participation. We will also conduct sensitivity analyses using 10-fold multiple imputation to assess the robustness of the results when missing data are imputed. The characteristics of non-responders will be summarized in our final report, and we will present the sensitivity of the estimated treatment effect due to alternative missing data methods

Aim 2: For this Aim, the primary outcome will be the difference in % of DSMES education sessions attended for participants who complete the study before and after the stakeholder convening. Additional endpoints will similarly assess the differences in the following metrics of participant engagement: % adherence to RT-CGM use, % of participants who complete all study visits, and % of eligible patients who enroll in the study.

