Randomization. The study biostatistician will generate a randomized sequence of treatment group assignments using stratified permuted-block randomization (random block sizes of 2, 4, 6) stratified by A1C >9.0% and ≤9.0%. Sequences will be stored at and delivered through the REDCAP study database at the UW. Research staff will obtain the next randomization once a potential study participant has been determined to be eligible and has signed the study consent form.

Vital signs, anthropometrics measurements, and demographic information will be collected, and participants will be asked to complete study surveys as further detailed below. Participants will be asked to use pedometers and keep them on their person as much as possible during waking hours. Baseline data will be collected no more than 3 weeks prior to the initiation of the DSMES curriculum, and pedometer data will be collected over 10 days immediately following the baseline study visit. Both groups will undergo blinded CGM with insertion by study personnel over the same 10 days following the baseline visit. Participants will then have a follow up visit from a Patient Navigator 10-14 days after the initial visit (detailed below) If less than 72 hours of CGM data is obtained at follow up PN visit participants will be asked to repeat blinded CGM. Participants will be asked to continue their customary dietary and exercise habits until initiation of the intervention

Follow-up study visits given in a community setting will be within an acceptable window for data collection and held at weeks 12+/-2 weeks and 24+/-2 weeks (Visits 2: end of education intervention and visit 3:12 weeks after education intervention. The same procedures will be completed as described in detail below. Visits 2 and 3 also may be held in the participant's home or Sea Mar clinic according to the participant's preference and be completed through a remote RC visit with a PN in person visit to complete blood pressure, weight circumference and weight and A1c. The study team will continue to contact withdrawn participants to conduct an interview regarding barriers to study engagement.

Study Procedures

The following procedures will be performed at baseline (visit 1), (Visit 2) and (Visit 3):

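### The RT-CGM contrast is not written out, and neither baseline adjustment nor the A1C stratum is specified; fitted as unadjusted change, it has less power than stated

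*Combined protocol and SAP*

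**What the plan says.** Section H (Randomization) describes permuted blocks of size 2, 4 and 6, "stratified by A1C >9.0% and ≤9.0" per cent.

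Section E (Data Analysis Plan, Aim 1) specifies a random-intercept, random-slope linear mixed model for A1C that "adjusts for an indicator of RT-CGM and time (baseline, visit 2, and visit 3) as fixed effects". Baseline A1C is thus one of the modelled responses, not a covariate. The other Aim 1 outcomes are to be handled in a similar way. The Aims 3 and 3A paragraph reuses this framework, says the RT-CGM coefficient will express the between-arm difference in change over 12 weeks, and adds survey language as the only further covariate. The stratum appears in no model.

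Aim 1 inference is directed at the change in the whole cohort, whatever the arm. The RT-CGM comparison is sized second: "the study is sized to detect a 0.6 difference in 12-week HbA1c between subjects randomized to RT-CGM vs blinded CGM", with power 0.82 at r=0.5 and 0.93 at r=0.7. The inputs are a "standard deviation in baseline A1C of 1.2 and a reduced standard deviation of 1.0 at 12 weeks", and the calculation proceeds "assuming a 15% reduction in the effect sample size (n=85) due to attrition", two-sided 0.05.

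**The concern.** Both arms receive the curriculum, so RT-CGM against blinded CGM is the only comparison that randomisation protects. The plan names its target (difference in 12-week change) but not the model term that estimates it. The omitted detail matters for two reasons.

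- A difference in change with separate baseline means per arm is less precise than a baseline-adjusted contrast whenever the correlation is moderate, as it is here.
- Stratified allocation makes the arms more alike on baseline A1C. An analysis that uses neither baseline A1C nor the stratum does not credit that balance, so its standard error is too large and its test conservative.

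At stake is whether the comparison has the stated power, and whether that depends on a choice still open when the data are seen.

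**Working it through.** **Inputs (Section E, Sample Size Estimation).** SD 1.2 at baseline and 1.0 at week 12; r = 0.5 or 0.7; difference 0.6; 85 evaluable, so 42.5 per arm; two-sided 0.05. Standard error = SD × √(2/42.5) = SD × 0.217. Power is from the noncentral t unless stated.

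**1. The plan's own figures.** The formula is not given. With SD = √((1.2² + 1.0²)/2) = 1.105 and residual SD = 1.105 × √(1 − r²):

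- r=0.5: SD 0.957, power 0.82
- r=0.7: SD 0.789, power 0.93

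Both stated figures are reproduced. A baseline-adjusted variance with SD 1.2 and n=100 also gives 0.82 and 0.93. At n=85, no variance tried without baseline adjustment gives both figures at two-sided 0.05; the week-12 value alone (SD 1.0) gives 0.78 for either r. The sizing therefore appears to presume baseline adjustment.

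**2. Unadjusted difference in change** (separate baseline means plus arm-by-time). Variance = 1.44 + 1.00 − 2.4r.

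- r=0.5: variance 1.24, SD 1.114, SE 0.242, power 0.69
- r=0.7: variance 0.76, SD 0.872, SE 0.189, power 0.88

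**3. Baseline-adjusted contrast**, using the plan's week-12 SD. Variance = 1.0² × (1 − r²).

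- r=0.5: variance 0.75, SD 0.866, SE 0.188, power 0.88
- r=0.7: variance 0.51, SD 0.714, SE 0.155, power 0.97

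The variance ratios are 1.24/0.75 = 1.65 and 0.76/0.51 = 1.49. Unadjusted change would need about 85 × 1.65 ≈ 141 or 85 × 1.49 ≈ 127 evaluable participants to match 85 with adjustment.

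**4. Baseline kept as a response, common mean across arms.** Generalised least squares with known covariance gives SE 0.188 and 0.155, identical to step 3 although no baseline covariate is listed.

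**5. Effect of ignoring the stratum.** The documents do not give the shape of the baseline distribution. Assume a gamma distribution shifted to start at 8, mean 9.3, SD 1.2, which puts about 48% above 9.0%. The stratum indicator then explains about 20% (r=0.5) or 17% (r=0.7) of the variance of change. The unadjusted SE is too large by 1/√(1 − 0.20) = 1.12 or 1/√(1 − 0.17) = 1.10.

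Simulations with stratified blocks, under assumed normal or skewed baselines, gave:

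- Unadjusted change: type I error about 0.03.
- Change plus stratum: power 0.78-0.81 (r=0.5) and 0.93-0.94 (r=0.7).
- Baseline-adjusted plus stratum: type I error about 0.05, power 0.88 and 0.97.

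Under the skewed baseline, removing the stratum from the baseline-adjusted model left power at 0.88 and 0.97.

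**6. Primary analysis.** With the paired change SDs of step 2 and n=85, the normal approximation gives 0.91 for a change of 0.4 (r=0.5) and 0.89 for 0.3 (r=0.7), in line with the stated 90%. None of the above alters this.

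**The case against.** The strongest reply is that baseline A1C is already in the likelihood. With RT-CGM and time as the only fixed effects, a single RT-CGM coefficient can mean a difference in 12-week change if it is zero for everyone at baseline. That is the common-baseline model, and it loses nothing. This stands: a reader might infer that leaving out a baseline covariate costs power in itself, and the documents do not support that. They leave the coding open.

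Other stronger readings also go too far:

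- *The comparison is underpowered as designed.* The stated figures fit a baseline-adjusted analysis, the plan regards r=0.5 as cautious, and Section D aims for 100 completers. With 100, even unadjusted change has power 0.76 and 0.93.
- *The RT-CGM coefficient is a diluted main effect.* Fitted literally to baseline and week 12 with no interaction, it would estimate 0.41 or 0.47 instead of 0.6, with power 0.52 or 0.60. The stated coding as a 12-week change argues against that reading.
- *The missing stratum is itself costly.* It matters only where baseline A1C is unused. An SE excess near 16% needs an untruncated normal baseline. Centred at 9.0 with SD 1.2, that puts about 20% of participants below the 8.0% entry floor.
- *Other outcomes lose as much.* No figure supports this. For equal SDs the variance ratio is 2/(1 + r), only 1.05 at an illustrative r=0.9.

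What survives is that the efficient model is one unstated option, while the ordinary difference-in-change fit falls below the stated power.

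**Conclusion.** The point holds as a specification gap, with moderate confidence. Under an unadjusted difference in change, power for 0.6 at n=85 is about 0.69 or 0.88 (r=0.5 or 0.7), which is 0.13 and 0.05 below the stated values, and the test is conservative. With baseline adjustment or a common baseline mean it is about 0.88 or 0.97.

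The power figures rest on the plan's own SDs, correlations and attrition. The 10-12% excess in the standard error rests on an assumed skewed baseline above 8. The documents do not show that the less efficient model will be used, so this is an improvement available at no cost in participants, not a demonstrated loss.

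**What to change.** For the RT-CGM contrast, write out one of these models:

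- (a) a longitudinal model with a common baseline mean, visit-specific RT-CGM effects and stratum-by-visit terms; or
- (b) an ANCOVA-type model with week-12 and week-24 A1C as responses, and arm, visit, arm-by-visit, continuous baseline A1C by visit, and the A1C stratum as fixed effects.

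Do not use baseline A1C as both covariate and response. Keep the existing longitudinal model, or use (a), for the whole-cohort change, which (b) cannot estimate. In (a), a stratum main effect alone would leave the contrast in change essentially as it was, hence the stratum-by-visit terms. The stratum is there to reflect the design; it adds almost no power for A1C once continuous baseline A1C is used.

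Adjust between-arm contrasts for secondary and Aim 3 outcomes for their own baseline values in the same way. The gain there cannot be quantified from the documents and may be small. State the power formula and SD that match the chosen model.

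The cost is SAP wording and a few degrees of freedom. Baseline A1C and the stratum are already collected.

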Baseline Visit/Visit 1. Base line visit is 2-4 weeks prior to Week 1, which is the start of education intervention. Week 1 is the first week of the education sessions. Baseline visit will occur in the participant's home or at a local Sea Mar clinic and/ or maybe a combination of remote and in-person. A research coordinator will review the full informed consent document, explaining study goals, procedures, and any potential risks in Spanish or English. Consent (appendix Z ?) will be obtained prior to any screening procedures being completed, and conducted in a quiet room or private televisit. Participant will be given ample time to ask questions, and a copy of the signed consent form will be given prior to start of screening visit procedures. Participants will fill out a contact form, including emergency contact (appendix Z1). Study staff will review medical history and medications and family history (appendix D), as well as all inclusion/exclusion criteria. Point of care A1C will be measured via point of care testing with a Siemens DCA Vantage A1C Analyzer, at LabCorp or quest for serum A1C if remote visit is completed. All women of child-bearing potential will undergo a urine pregnancy test either point of care or at LabCorp. Participants who meet criteria for enrollment and wish to proceed with study participation will be randomized to an intervention arm in unblinded fashion.

Remote Consent : If baseline visit is remote/virtual, the consent form will be sent to the participant via REDCap to be viewed and signed remotely. Subjects can also request that a paper copy of the consent be mailed to them before Visit 1. The informed consent discussion includes time for the potential participant to read over the consent form and to think about their questions. If the potential participant has questions outside of the Research Coordinator's scope, the potential participant will be offered a follow-up consultation with the Principal Investigator or Co-Investigator who can provide more information. As this is a minimal risk study, we will request a waiver of documentation of consent.

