Anthropometric and vital sign measurements: **Height** will be measured by a Stadiometer. **Weight** will be measured using a SECA Digital scale, and BMI (kg/m^2) will be calculated. **Waist circumference** will be measured using a flexible measuring tape. Participants will remain in a seated position for a minimum of 15 minutes prior to measurement of **resting heart rate** and **blood pressure** with an Omron Professional Digital blood pressure and heart rate monitor.

Concomitant medications: Participants will be instructed to bring all current medications (prescription, over the counter, and herbal or vitamin supplements) to each study visit. The research study coordinator will review and record these medications. Comorbidities: We will use patient self-report to document stroke, CVD (congestive heart failure, myocardial infarction, or coronary heart disease), peripheral vascular disease, peripheral neuropathy, renal disease, and retinopathy. Point of Care A1C: The DCA Vantage Analyzer tests for a quantitative determination of A1C in human whole blood and provides immediate test results from a finger prick of blood. If age <50 and female urine dipstick for pregnancy completed.

Pedometer: participants will be given a pedometer or if preferred use the one available on their smartphone. They will be asked to keep the pedometer or phone on them as much as possible during waking hours during the study. Data will be collected for 10 days after the first visit then for the 10 days prior for visits 2 and 3.

Continuous Glucose Monitoring:

Blinded CGM: All participants will undergo blinded CGM for 10 days at baseline a (2-4 weeks prior to start of education) and visit 3 (24 weeks [+/-2 weeks]). The blinded CGM- education group will also complete blinded CGM for 10-day period at the end of the education intervention (visit 2: study weeks12 [+/-2 weeks]). Participants can mail blinded CGM devices back in self-addressed postage-paid envelopes provided at the initial PN visit and devices will be provided at the first PN visit.

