CGM (DEXCOM G6): A continuous glucose monitor (CGM) is a way to measure glucose levels in real-time throughout the day and night. A tiny electrode called a glucose sensor is inserted under the skin by a skin prick to measure glucose levels in tissue fluid. A small plastic piece of tubing remains inserted in the skin. Typically, one cannot feel this tubing once inserted. It is connected to a transmitter that sits on top of the skin and is about the size of a quarter. It is attached or secured by medical tape to the wearer's skin. It is approved for use on the abdomen and has been shown to be effective for use on alternative sites such as upper buttock and arm for 10 days. The CGM either records the blood sugars and stores which we will then be mailed or returned at education session one or it sends the information via wireless radio frequency to a monitoring/display device or to a cellular phone so one can see their own data on their glucose, and we can download it remotely. The device automatically generates an alert for glucose < 55, and an alert will also be generated for glucose > 180 in the unblinded portion of the study. The intervention group participants will be given a handout (Appendix K) for troubleshooting these alerts, particularly during the blinded portion of the study. DEXCOM G6 is FDA approved for use in patients with diabetes and will be used in accordance with instructions as approved for diabetes. The risk is minimal with use of this device. In this study, we recommend patients connect the CGM to their cell phones. Study staff will insert the first sensor for the groups and then PN at digital navigation visit will demonstrate how to insert additional sensors for the intervention group who will continue to use RT-CGM and control group in case they need to self-insert blinded CGM. If this is to be done as a televisit, the sensors, transmitter, and device (if needed) will be mailed to the participant. Then the study staff will walk the participant through the first insertion through a virtual zoom visit. Patients will also have a YouTube video available for reference for the patients. The patients will be instructed on how to remove the sensor themselves after 10 days and bring it back or mail back. The RT-CGM-education intervention group will wear the RT-CGM- cyclically and have telephone support and may refer to the YouTube video on insertion if needed. The intervention participants will have RT-CGM download after 3 cyclic sessions of use and at 5 sessions of use. The Blinded-CGM education group participants will wear the blinded CGM at baseline and 24=/- weeks at conclusion of intervention. If, during the blinded portion of the study, due to device malfunction (rather than subject non-compliance), the device records less than 3 days of data, the participant will restart another 10 days of blinded CGM data.

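### The baseline windows contradict each other, and under the 3-week cap a repeated blinded CGM usually runs past the first class, with no rule keeping those days out of baseline

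*Combined protocol and SAP*

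**What the plan says.** Four places give the timing of baseline.

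- Aim 1, in the opening summary: "baseline(0-4 weeks".
- Section H, Baseline Visit/Visit 1: "Base line visit is 2-4 weeks prior to Week 1, which is the start of education intervention".
- Section H, Randomization: "Baseline data will be collected no more than 3 weeks prior to the initiation of the DSMES curriculum".
- Section H, Continuous Glucose Monitoring: "All participants will undergo blinded CGM for 10 days at baseline a (2-4 weeks prior to start of education".

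The first recording is fixed by Section H, Randomization: "Both groups will undergo blinded CGM with insertion by study personnel over the same 10 days following the baseline visit". A Patient Navigator visit follows 10 to 14 days after visit 1, and there the repeat rule applies: "If less than 72 hours of CGM data is obtained at follow up PN visit participants will be asked to repeat blinded CGM". That paragraph gives no length for the repeat.

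The device description (Medical Devices, Dexcom G6) has a second repeat rule. It applies only when, "due to device malfunction (rather than subject non-compliance), the device records less than 3 days of data", and it sets a fresh 10-day recording. The same description covers how blinded data come back: the device "stores which we will then be mailed or returned at education session one".

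Section N bases the between-group CGM comparisons on change from baseline to week 12 and to week 24.

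**The concern.** There are two problems, and the second follows partly from the first.

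Site staff cannot satisfy all the windows. A visit 22 to 28 days before the first class is allowed by the Baseline Visit paragraph and by the CGM paragraph, and is ruled out by the cap in the Randomization paragraph.

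The repeat rule also needs calendar time that the capped window mostly does not provide. A recording that runs into the classes is no longer a pre-intervention measurement, yet the plan has no latest date for a repeat, no delay of class 1 or of the first real-time wear, and no analysis rule for late days. The Randomization paragraph itself asks participants to keep their usual diet and exercise until the intervention starts, so a late repeat defeats the purpose of the recording.

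At stake is the reference value for time in range, mean glucose, variability and the other CGM indices at both follow-up visits. In the RT-CGM arm a late repeat might also meet the first real-time wear. The participant would then either start the intervention late or see glucose values during what is recorded as baseline.

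**Working it through.** The plan states no figure that depends on this point, so there is none to reproduce. The check is calendar arithmetic, with day 0 as the first class.

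**Inputs**

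- Lead L, in days from visit 1 to class 1: 14 to 28 (Baseline Visit; CGM paragraph), or 14 to 21 once the 3-week cap is also applied.
- Navigator visit day N: 10 to 14 after visit 1 (Randomization).
- Repeat length W: 10 days (device description, stated there for malfunction only). W = 3 is a sensitivity check, because 72 hours is the sufficiency threshold.
- Assumption: the repeat starts at the navigator visit.

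**Formula**

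End of repeat relative to class 1 = N + W − L. It fits if this is 0 or less.

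With W = 10, N + W runs from 10 + 10 = 20 to 14 + 10 = 24 days after visit 1. A repeat therefore never fits for L below 20, always fits for L of 24 or more, and depends on N in between.

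| Lead L | End of repeat (N = 10 to N = 14) | Allowed by 2-4 weeks | Allowed by 3-week cap |
|---|---|---|---|
| 14 | +6 to +10 | yes | yes |
| 20 | 0 to +4 | yes | yes |
| 21 | −1 to +3 | yes | yes |
| 24 | −4 to 0 | yes | no |
| 28 | −8 to −4 | yes | no |

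**All whole-day combinations of L and N**

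| Window | W = 10 fits | W = 3 fits |
|---|---|---|
| Both rules, L = 14 to 21 (8 × 5 = 40) | 3 | 34 |
| 2-4 weeks alone, L = 14 to 28 (15 × 5 = 75) | 35 | 69 |
| Part removed by the cap, L = 22 to 28 (7 × 5 = 35) | 32 | 35 |

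The three that fit under both rules are L = 20 with N = 10, and L = 21 with N = 10 or 11. These counts show how much room the rules leave. They are not probabilities, because the documents give no distribution of visit dates.

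**First recording.** It ends at 10 − L, which is day −4 at the latest for L of 14 or more. The original 10-day recording is therefore not at issue under either window.

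**First real-time wear.** Section H gives cycles of 10 days on and 7 off but no first day. Two anchors bracket it.

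- Start at class 1: wears begin on days 0, 17, 34, 51 and 68. Every late repeat then overlaps the first wear.
- Count back from a last wear starting at session 12 (day 11 × 7 = 77): wears begin on days 9, 26, 43, 60 and 77. Only a repeat ending on day +10 then overlaps.

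The protocol also places completion of the third wear near session 6 (day 5 × 7 = 35). A class-1 start completes it on day 34 + 10 = 44 and a day-9 start on day 43 + 10 = 53, so that anchor leans towards the earlier start without settling it.

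**Navigator window.** With L = 14 to 21 the navigator visit falls between 14 − 14 = 0 and 21 − 10 = 11 days before class. The preparation paragraph puts navigator contact at no more than 2 to 4 weeks before class. If that is meant as a window, the two do not match. If it is only an upper limit, they do.

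**The case against.** A reader might infer that the repeat can never be finished before the intervention, and that the overlap biases the comparison between arms. The case against both inferences is good.

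- **Never is wrong.** The 2-to-4-week window alone always accommodates a 10-day repeat for visits 24 to 28 days ahead, and even with the cap three combinations fit.
- **The 10-day length is borrowed.** The Randomization paragraph states none. Three days of data would meet the plan's own threshold, and a 3-day repeat fits in 34 of 40 combinations under both rules. This stands, but no passage allows a shortened repeat, and the only length written down is 10 days.
- **The meeting with real-time wear is not established.** Its first day is not stated, and on one reading almost no repeat reaches it.
- **Bias between arms is not shown.** Both arms attend the same classes, so class overlap alone is common to both. A differential effect would have to come from the real-time wear, and neither its direction nor its size can be derived from the documents.
- **Late discovery may be avoidable.** The CGM Ancillary Devices paragraph has CLARITY transferring data to the site in blinded as well as real-time mode, so handing the device in at the first class need not be when a shortfall is first seen.
- **The reach is small.** Only participants with under 72 hours of data are touched, and the between-group CGM changes are largely descriptive in Section E, although time in range is also modelled. Section T pays for up to two unscheduled visits for lost CGM data, so the sponsor expects some, but gives no rate.

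The objection does not remove the contradictory windows, the two different triggers, or the absence of any rule for wear days recorded after the intervention starts.

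**Conclusion.** The concern holds in a limited form. The baseline windows conflict as written, which needs no assumption to show. If the 3-week cap is applied and the repeat lasts 10 days from the navigator visit, it ends between 1 day before and 10 days after class 1, so it usually overlaps the classes. Without the cap, whether it overlaps depends on when visit 1 falls. In the RT-CGM arm, overlap with the first real-time wear is possible but undetermined. The plan as written lets such days serve as the baseline for the week-12 and week-24 CGM changes.

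The two repeat triggers also disagree: any cause in the Randomization paragraph, malfunction only in the device description. For a participant who simply did not wear the sensor, one rule orders a repeat and the other does not.

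The effect is confined to secondary CGM outcomes and to participants who need a repeat, whose share is not stated. The overlap does not touch A1C, the primary outcome, which is measured at the visit itself. The documents do not support calling the repeat impossible or the arm contrast biased. This should be corrected, but it does not threaten the trial's main result.

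**What to change.** - Reconcile the four statements of the baseline window (Aim 1; Section H under Baseline Visit, Randomization and Continuous Glucose Monitoring) into one that leaves room for a possible repeat. Reconcile that with the navigator preparation window in the same section.
- Use one repeat trigger and one repeat length in the Randomization paragraph and the device description.
- Check that blinded data are sufficient at the navigator visit, by download or through CLARITY, rather than waiting for the device at class 1.
- State in Sections E and N that only wear days before class 1 and before the first RT-CGM insertion count as baseline, with the existing 72-hour minimum applied to those days.

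The last item removes the contamination by itself. Even with visits 14 to 21 days ahead, a repeat begun at the navigator visit leaves at least 3 days before class in 34 of the 40 combinations. It is therefore not necessary to force every baseline visit into a narrow 24-to-28-day slot.

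The cost is protocol wording, slightly tighter scheduling within each cycle, and a few baseline CGM values that are missing rather than contaminated. If the sponsor reconciles the windows by relaxing the cap, all baseline measurements, including A1C, may be taken somewhat earlier before class; that trade-off is the sponsor's to weigh.
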